3.3.2. EXCLUSION CRITERIA

1. Subjects who have undergone a successful revascularization procedure or sympathectomy within 12 weeks prior to study entry. A clinically *unsuccessful* revascularization procedure is defined as one in which:
 - the target vessel re-occludes ($\geq 50\%$, as verified by a second angiogram. Duplex ultrasonography can be used to determine vessel patency if the patient cannot tolerate a second angiogram), or
 - the target vessel remains patent, but there is no resolution of symptoms 6 weeks after the procedure (e.g. no evidence of ulcer healing, no improvement in pressures, no reduction in resting pain);

-
2. Subjects that will require an amputation in the target leg within 4 weeks of randomization;
 3. Subjects with evidence of active infection (e.g., cellulitis, osteomyelitis) or deep ulceration exposing bone or tendon in the extremity planned for treatment;
 4. HF with a NYHA classification of III or IV;
 5. Stroke (NIH scale > 2) or myocardial infarction within last 3 months;
 6. Unstable angina
 7. Uncontrolled hypertension defined as sustained systolic blood pressure (SBP) > 200 mmHg or diastolic BP (DBP) > 110 mmHg at baseline/screening evaluation;
 8. Ophthalmologic conditions pertinent to proliferative retinopathy or conditions that preclude standard ophthalmologic examination;
 9. Inflammatory disorder of the blood vessels (inflammatory angiopathy, such as Buerger's disease);
 10. Subjects with advanced liver disease including decompensated cirrhosis, jaundice, ascites or bleeding varices;
 11. Subjects currently receiving immunosuppressive medications chemotherapy, or radiation therapy;
 12. Positive HIV or HTLV at Screening;
 13. Active Hepatitis B or C infection as determined by Hepatitis B surface antibody (HBsAb), Hepatitis B core antibody (IgG and IgM; HBcAb), Hepatitis B surface antigen (HBsAg) and Hepatitis C antibodies (Anti-HCV), at Screening;
 14. Specific laboratory values at Screening including: Hemoglobin < 8.0 g/dL, WBC < 3,000 cells per microliter, platelet count < 75,000/mm³, AST and/or ALT > 3 times the upper limit of normal or any other clinically significant lab abnormality which in the opinion of the investigator should be exclusionary;
 15. Patients with a recent history (< 5 years) of or new screening finding of malignant neoplasm except basal cell carcinoma or squamous cell carcinoma of the skin (if excised and no evidence of recurrence); patients with family history of colon cancer in any first degree relative are excluded unless they have undergone a colonoscopy in the last 12 months with negative findings;
 16. Elevated PSA unless prostate cancer has been excluded;
 17. Subjects with any co-morbid conditions likely to interfere with assessment of safety or efficacy or with an estimated life expectancy of less than 6 months
 18. Subjects requiring > 81 mg daily of acetylsalicylic acid; If > 81 mg are taken at screening, subjects may be enrolled if willing/able to switch to another medication for the duration of the study;
 19. Subjects requiring regular COX-2 inhibitor drug(s) or high dose steroids (excepting inhaled steroids);
 20. Major psychiatric disorder in past 6 months;
 21. History of drug or alcohol abuse / dependence in the past 2 years;
 22. Use of an investigational drug or treatment in past 12 months; concurrent participation in investigational protocol or unapproved therapeutics; and
 23. Unable or unwilling to give informed consent.
-

3.4. STUDY PROCEDURES

Prior to recruitment of any patients into the study, written approval of the protocol and informed consent must be obtained from the Institutional Review Board (IRB).

3.4.1. INFORMED CONSENT

The investigator will explain the study purpose, procedures, and patient's responsibilities to the potential participant. The patient's willingness and ability to meet the follow-up requirements will be determined and written informed consent will be obtained (Appendix 2). The patient will sign and date the informed consent form. The person executing the consent will also sign and date the consent form. The original informed consent form will be retained with the patient records; a copy will be provided to the patient.

Following is a detailed list of study visits from screening to final follow-up and the required procedures / tests. Methodologies for specific tests/ procedures are described in Section 4.

3.4.2. PATIENT IDENTIFICATION

To maintain confidentiality, the patient's name should not be recorded on any study document other than the informed consent form. All patients that give informed consent (sign the informed consent form) will be assigned a unique identifier.

3.4.3. SCREENING (DAY -60 TO DAY 0)

Patient enrollment is subject to the rules established in Section 3.2 for randomization, but screening procedures can proceed provided the Investigator waits for enrollment confirmation from ViroMed or its Designee.

The following procedures / evaluations will be conducted at screening:

- Obtain informed consent prior to any study-related procedures
- Evaluation of eligibility
- Complete Medical History
- Vital Signs
- Complete Physical Exam
- Concomitant Medications
- Cancer screening – including cancer markers (carcinoembryonic antigen (CEA), alpha fetoprotein (AFP), CA19-9, and CA125 (females only)); pap smear and mammogram if not performed within past 12 months (females only); chest X-ray or CT scan of the chest (if the patient has a previous history of tobacco use, a CT scan will be performed instead of the chest X-ray) within 3 months prior to study entry; PSA (males only); for patients ≥ 50 years old, colonoscopy within past 10 years
- Retinal Fundoscopy - fluorescein angiography may be conducted in cases where funduscopy alone is deemed insufficient
- Viral screening – HIV, Anti-Human T-Cell Lymphotropic Virus (HTLV)

-
- Positive Hepatitis B or C as determined by Hepatitis B core antibody (HBcAB), antibody to Hepatitis B antigen (IgG and IgM; HbsAB), Hepatitis B surface antigen (HBsAg) and Hepatitis C antibodies (Anti-HCV), at Screening
 - Serum chemistry and hematology
 - Urinalysis
 - Urine pregnancy test (for women of childbearing potential only)
 - Photograph and measurement of ulcer(s) – if present
 - ECG
 - Visual Analog Scale (VAS) score
 - ABI & TBI
 - TcPO₂

3.4.3.1. SCREEN FAILURES

Patients not meeting all study entry criteria will be designated as a screen failures. End of study procedures will not be performed for these patients, but their reason for discontinuation will be recorded on the CRF. Screen failures will be replaced.

3.4.4. TREATMENT AUTHORIZATION

After providing written informed consent, potential study participants will undergo Screening assessments. The site will complete a Treatment Authorization Form (TAF) for patients determined to be eligible for study participation. The TAF includes the patient identification number, demographic information (gender, date of birth) and indication that the patient meets all inclusion and exclusion criteria. The completed TAF will be faxed to ViroMed or its designee. ViroMed or its designee will confirm whether the patient can be treated, update the TAF with specific treatment instructions, and return it to the investigational site by fax. Upon receipt, the Investigator will schedule the patient to undergo the study treatment. Note: adherence to this process is mandatory to track enrollment and to assure proper randomization.

3.4.5. RANDOMIZATION & BLINDING

A randomization schedule with subjects allocated to high dose, low dose or control in a 2:2:1 ratio will be sent to a centralized drug depot, which will prepare individual kits that are sequentially numbered and contain the appropriate treatment based on the randomization schedule. When a site identifies a subject and treatment authorization is granted, the site will notify the drug depot.

The drug depot will:

1. Send the next kit in sequence to the site, labeled with the site number and subject number.
2. Record which kit number was assigned to which site/subject and the date.
3. Include in the kit, a sealed envelope that identifies the site number, subject number and kit number on the outside and the assigned treatment inside, to be opened by the Investigator or designee only in the case of a medical emergency.

-
4. Send another sealed envelope to the Sponsor with the site number, subject number and kit number on the outside and the assigned treatment inside, to be opened by the Sponsor or designee only in the case of a medical emergency.

Blinding will be achieved by having the study medication (VM202) prepared by the study pharmacist. Reconstituted VM202 is indistinguishable from saline solution. The site pharmacist prepares the vials according to the instructions in the kit (which vials to reconstitute with water for injection [WFI]. The drug depot, site pharmacist and select individuals at Synteract (but not including study monitors) will be unblinded to the treatment assignments. The subject and study personnel, including core lab, investigator and study coordinators, will remain blinded until all data has been entered into the database and the database is locked.

IN CASE OF EMERGENCY ONLY, i.e. SERIOUS ADVERSE EVENT (SAE) AND ONLY WHEN THIS INFORMATION INFLUENCES THE PATIENT'S MANAGEMENT, the Investigator may open the sealed envelope to immediately start the appropriate treatment (to be recorded in the case report form [CRF]).

For each opened envelope, the Investigator will provide the name of the person who opened the envelope, reason, date, and signature on the envelope. At the end of the study, all (opened and unopened) envelopes will be returned with the study products to the Sponsor.

3.4.6. DAY 0 – 1ST INJECTIONS

3.4.6.1. PRE-INJECTION (WITHIN 4 HRS PRIOR TO INJECTIONS)

- Concomitant Medications
- Vital Signs
- Serum Chemistry and hematology
- Serum HGF
- Copies of VM202 in whole blood
- Visual Analog Scale (VAS) score
- VascuQol
- ABI & TBI
- TcPO₂
- Photograph and measurement of ulcer(s) – if present
- MRA – sub-study to be only at designated site(s) –to be completed within 7 days prior to Day 0

3.4.6.2. 1ST DOSE OF VM202 / PLACEBO

- Intramuscular injections of VM202 in calf (unilateral)

3.4.6.3. POST-INJECTION

- Vital Signs
- Copies of VM202 in whole blood (2 hours ± 1 hour post injection)

-
- Injection site assessment
 - Adverse event assessment

3.4.7. DAY 14 ± 3 DAY –2ND INJECTIONS

3.4.7.1. PRE-INJECTION (WITHIN 4 HRS PRIOR TO INJECTIONS)

- Concomitant Medications
- Vital Signs
- Serum Chemistry and hematology
- Visual Analog Scale (VAS) score
- Photograph and measurement of ulcer(s) – if present
- Injection site assessment
- Adverse event assessment

3.4.7.2. 2ND DOSE OF VM202 / PLACEBO

- Intramuscular injections of VM202 in calf (unilateral, same leg as 1st injection)

3.4.7.3. POST-INJECTION

- Vital Signs
- Injection site assessment
- Adverse event assessment

3.4.8. DAY 28 ± 3 DAY –3RD INJECTIONS

3.4.8.1. PRE-INJECTION (WITHIN 4 HRS PRIOR TO INJECTIONS)

- Concomitant Medications
- Vital Signs
- Serum Chemistry and hematology
- Visual Analog Scale (VAS) score
- ABI & TBI
- Photograph and measurement of ulcer(s) – if present
- Injection site assessment
- Adverse event assessment

3.4.8.2. 3RD DOSE OF VM202 / PLACEBO

- Intramuscular injections of VM202 in calf (unilateral, same leg as 1st injection)

3.4.8.3. POST-INJECTION

- Vital Signs
- Injection site assessment
- Adverse event assessment

3.4.9. DAY 42 ± 3 DAY – 4TH INJECTIONS

3.4.9.1. PRE-INJECTION (WITHIN 4 HRS PRIOR TO INJECTIONS)

- Concomitant Medications
- Vital Signs
- Serum Chemistry and hematology
- Serum HGF
- Copies of VM202 in whole blood
- Visual Analog Scale (VAS) score
- Photograph and measurement of ulcer(s) – if present
- Injection site assessment
- Adverse event assessment

3.4.9.2. 4TH DOSE OF VM202 / PLACEBO

- Intramuscular injections of VM202 in calf (unilateral, same leg as 1st injection)

3.4.9.3. POST-INJECTION

- Vital Signs
- Copies of VM202 in whole blood (2 hours ± 1 hour post injection)
- Injection site assessment
- Adverse event assessment

3.4.10. DAY 49 ± 3 DAYS

- Concomitant Medications
- Vital Signs
- Serum Chemistry and hematology
- Copies of VM202 in whole blood
- Serum HGF
- Photograph and measurement of ulcer(s) – if present
- Injection site assessment
- Adverse event assessment

3.4.11. DAY 90 ± 7 DAYS

- Concomitant Medications
- Vital Signs
- Serum Chemistry and hematology
- Serum HGF
- Copies of VM202 in whole blood
- Visual Analog Scale (VAS) score
- VascuQol
- ABI & TBI

-
- Photograph and measurement of ulcer – if present
 - Adverse event assessment

3.4.12. 6 MONTHS ± 1 MONTH

- Concomitant Medications
- Vital Signs
- Serum Chemistry and hematology
- Photograph and measurement of ulcer – if present
- Visual Analog Scale (VAS) score
- Copies of VM202 in whole blood
- ABI & TBI
- TcPO₂
- MRA – sub-study to be only at designated site(s) - to be completed within 7 days of the Month 6 Visit
- Rutherford Classification
- Adverse event assessment

3.4.13. 9 MONTHS ± 1 MONTH

- Concomitant Medications
- Vital Signs
- Serum Chemistry and hematology
- Visual Analog Scale (VAS) score
- VascuQol
- ABI & TBI
- Photograph and measurement of ulcer(s) – if present
- TcPO₂
- MRA – sub-study to be only at designated site(s)) - to be completed within days of the Month 9 Visit
- Rutherford Classification
- Adverse event assessment

3.4.14. 12 MONTHS ± 1 MONTH

- Retinal fundoscopy
- Concomitant Medications
- Vital Signs
- Serum Chemistry and hematology
- Visual Analog Scale (VAS) score
- VascuQol
- ABI & TBI
- Photograph and measurement of ulcer(s) – if present
- TcPO₂
- Rutherford Classification
- Adverse event assessment

3.5. STUDY COMPLETION

3.5.1. COMPLETED PATIENTS

Each patient in the study will be considered completed when all assessments through 12 months have been performed in accordance with the study protocol.

3.5.2. DISCONTINUED PATIENTS

Any patient may voluntarily discontinue the study at any time without prejudice. The investigator may discontinue a patient from the study at any time if (s)he considers that remaining in the study compromises the patient's health or the patient is not sufficiently cooperative. In either event, reason(s) for discontinuation should be recorded on the CRF.

Possible reasons for study discontinuation include the following:

- AEs necessitating discontinuation from the study (pre-treatment).
- The patient is lost to follow-up.
- Patient decision (specify).
- Investigator decision (specify).
- Other reason (specify).

The reasons for any patient discontinuation will be recorded on the study completion form of the CRF.

Discontinued patient(s) will be replaced in any treatment arm if discontinuation occurs prior to the 90 Day follow-up;

Patients discontinued for AE(s) will be followed-up after patient's discontinuation until the event is resolved or considered medically stable by the investigator.

Subjects that withdraw prior to study completion will undergo the following if possible:

- Retinal Fundoscopy
- Concomitant Medications
- Serum Chemistry and hematology
- Photograph and measurement of ulcer(s) if present at baseline
- Vital Signs
- Serum HGF if discontinued prior to Day 90
- Copies of VM202 in whole blood if discontinued prior to Day 90
- Injection site reaction assessment if discontinued prior to Day 49
- Adverse Events

In case of a patient lost-to-follow-up, the investigator must do his/her best to contact the patient (by phone or letter) at least twice. If no response is obtained from the patient, the investigator is encouraged to contact one of the patient's relatives or his/her general practitioner. The evidence of these contacts must be recorded in the patient medical chart. It can be, for instance, the acknowledgement of receipt of a letter sent to the patient.

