5.3. REPORTING/RECORDING OF AEs

Throughout the course of the study, all efforts will be made by the investigator to remain alert to possible AEs. The first concern will be the safety of the patient, and for providing appropriate medical intervention. The period of observation for collection of AEs starts during the first intramuscular injection procedure (Day 0) until the 12 month follow-up visit. Any AE should be recorded on the appropriate CRF page(s).

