6.2.2. SECONDARY EFFICACY ENDPOINTS

Other secondary endpoints will include:

- Difference in pain level between baseline and the 9 month follow-up as determined by VAS by sex and by comorbidities (esp. diabetes or renal dysfunction)
- Change in tissue oxygenation (TcPO₂) from baseline to 6, 9 and 12 months following the first treatment
- Change in hemodynamic measures (ABI and TBI) from baseline to Day 28, Day 90, 6 months, 9 months and 12 months following the first treatment
- Change in perfusion (MRA) from baseline to 9 months following the first treatment
- Wound healing (no ulcer: change of skin condition, one ulcer: change of ulcer size, multiple ulcer: change of ulcer number) from baseline to 9 months following the first treatment
- Change in VAS score from baseline to Day 14, Day 28, Day 42, Day 90, at 6 months, 9 months, and 12 months.
- Change in QOL score (VascuQol) at 90 Days, 9 months and 12 months;
- Major limb amputation rate at six months and twelve months following the first treatment
- Mortality at six and twelve months after first treatment

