10.2.7. Amputation and Mortality Rate

The rates of amputation, limb salvage and mortality will be analyzed for all treated subjects per actual treatment using the method for time-to-event variables. The probability of being event-free at 6 and 12 months will be summarized for each treatment arm and compared vs. Placebo using a Log Rank test.

The duration of time to amputation will be defined as the number of days between the day of amputation – the first dose date + 1. If a subject does not report amputation, then the date that the subject will be censored at the date of study discontinuation. If the date of study discontinuation is not available, then the subject's censor date will be the last known visit the subject attended. The same calculation will be repeated for limb salvage and mortality (time to death).

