APPENDIX B: TABLE LAYOUTS

Table 1
Subject Disposition
All Subjects

	Placebo	VM202- 8 mg	VM202- 16 mg
Subjects Enrolled	n (Overall)		
ITT Population ^[1]	n	n	n
Safety Population ^[2]	n (%)	n (%)	n (%)
Per-Protocol Population ^[3]	n (%)	n (%)	n (%)
Received All Planned Doses of VM202?			
Yes	n (%)	n (%)	n (%)
No	n (%)	n (%)	n (%)
Last Visit Attended			
Any Visit Prior to Visit- Day 0	n (%)	n (%)	n (%)
Visit- Day 0	n (%)	n (%)	n (%)
Visit- Day 14	n (%)	n (%)	n (%)
Visit- Day 28	n (%)	n (%)	n (%)
Visit- Day 42	n (%)	n (%)	n (%)
Visit- Day 49	n (%)	n (%)	n (%)
Visit- Day 90	n (%)	n (%)	n (%)
Visit- 6 Months	n (%)	n (%)	n (%)
Visit- 9 Months	n (%)	n (%)	n (%)
Visit- 12 Months	n (%)	n (%)	n (%)
Completed Study?			
Yes	n (%)	n (%)	n (%)
No	n (%)	n (%)	n (%)

Note: Percentages based on number of subjects in the ITT population.

[1] All subjects who were randomized regardless of whether treatment was received.

[2] All subjects who received at least one dose of study drug.

[3] All subjects who received the correct dose of study drug medication, have the 9-month VAS assessment, and do not have any protocol violations or major deviations.

path\program.sas date time

Table 1
Subject Disposition
All Subjects

	Placebo	VM202- 8 mg	VM202- 16 mg
Primary Reason for Discontinuation			
Screen failure	n (%)	n (%)	n (%)
Lost to Follow-up	n (%)	n (%)	n (%)
Adverse Event	n (%)	n (%)	n (%)
Non-compliance	n (%)	n (%)	n (%)
Subject withdrew consent	n (%)	n (%)	n (%)
Principal Investigator decision	n (%)	n (%)	n (%)
Subject requires intervention for treatment of acute limb ischemia	n (%)	n (%)	n (%)
Death	n (%)	n (%)	n (%)
Other	n (%)	n (%)	n (%)

Note: Percentages based on number of subjects in the ITT population.

[1] All subjects who were randomized regardless of whether treatment was received.

[2] All subjects who received at least one dose of study drug.

[3] All subjects who received the correct dose of study drug medication, have the 9-month VAS assessment, and do not have any protocol violations or major deviations.

path\t_program.sas date time

Table 2.1
Demographic and Baseline Characteristics
ITT Population

	Placebo (N=)	VM202- 8 mg (N=)	VM202- 16 mg (N=)	p-value
Age (years) ^[1]				
N	n	n	n	
Mean (SD)	xx.x (xx.xx)	xx.x (xx.xx)	xx.x (xx.xx)	x.XXXX ^[2]
Median	xx.x	xx.x	xx.x	
Min, Max	xx, xx	xx, xx	xx, xx	
Sex				x.XXXX ^[3]
Male	n (%)	n (%)	n (%)	
Female	n (%)	n (%)	n (%)	
Race				x.XXXX ^[3]
Caucasian	n (%)	n (%)	n (%)	

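### Dosed patients who leave early have no required death or major-amputation status to Month 12 and are censored at discontinuation, so the 6- and 12-month estimates may be biased

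*Protocol*

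**What the plan says.** **After exit.** Protocol 3.5.2 introduces the exit assessments with "Subjects that withdraw prior to study completion will undergo the following if possible". The list covers fundoscopy, laboratory tests, ulcers, vital signs and adverse events, and Appendix 1 shows it as a single Early Withdrawal column. Patients discontinued for an adverse event are followed "until the event is resolved or considered medically stable by the investigator". Protocol 5.2 and 5.4.1 extend follow-up to resolution or stability to every recorded AE and SAE. For patients lost to follow-up, 3.5.2 asks for at least two contact attempts, after which "the investigator is encouraged to contact one of the patient's relatives or his/her general practitioner". The attempts must be documented, but no outcome to collect is specified.

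**Nominal window.** Protocol 5.3 states that AE collection "starts during the first intramuscular injection procedure (Day 0) until the 12 month follow-up visit". It gives no means of reaching a patient who has left.

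**Early exits are expected.** Protocol 3.5.2 states: "Discontinued patient(s) will be replaced in any treatment arm if discontinuation occurs prior to the 90 Day follow-up".

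**Endpoints.** Protocol 6.2.2 lists "Major limb amputation rate at six months and twelve months following the first treatment", and mortality at the same two times.

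**Analysis.** SAP 10.2.7 uses Kaplan-Meier estimates and log-rank tests in treated patients. For a patient with no reported amputation, "then the date that the subject will be censored at the date of study discontinuation", or at the last visit attended if that date is missing. The same rule applies to limb salvage and death.

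**Exit reasons.** Protocol 3.5.2 lets the investigator remove a patient whose health would be compromised by staying. The SAP Table 1 shell (Appendix B) lists adverse event, investigator decision, death and "Subject requires intervention for treatment of acute limb ischemia".

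**The concern.** Kaplan-Meier estimation treats a censored patient as having the same later risk as those still under observation. That is doubtful when the reason for leaving is an adverse event, an investigator's judgement about health, or an acutely ischaemic limb. If such leavers go on to die or lose the limb at a higher rate, and nobody is required to find out, the 6- and 12-month estimates lose events selectively. If exits differ between arms, the comparison with placebo is affected too.

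The loss of information matters even without bias. The arms are 20, 20 and 10 patients, safety is the SAP's primary objective, and the SAP plans no sensitivity analysis for informative censoring. Outcomes not collected at the time may not be recoverable later.

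**Working it through.** The plan gives no figure for exits or for the effect of censoring, so there is none to reproduce. The following is an illustration, using mortality because the SAP analyses it directly.

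**Inputs**
- True 12-month mortality: 25%, the approximate figure in Protocol 1.3.3.
- Exits over 12 months: 20% (assumption; range 10% to 30%).
- Ratio *r* of the death hazard after exit to that before exit: 0.5 to 5 (assumption).
- Arm sizes: 20, 20 and 10 (SAP 4).

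**Model** (time in years, constant hazards *h* for death before exit and *c* for exit)
- Exit hazard: c = −ln(1 − 0.20) = 0.2231.
- Deaths seen before exit: S = h/(h + c) × (1 − e^(−(h + c))).
- Deaths after exit, not seen: U = ∫₀¹ c·e^(−(h + c)t) × (1 − e^(−r·h·(1 − t))) dt.
- *h* is solved so that S + U = 0.25.
- With censoring at exit, Kaplan-Meier estimates 1 − e^(−h) in large samples.

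Example for r = 2: h = 0.2624. S = 0.2624/0.4855 × (1 − e^(−0.4855)) = 0.208 and U = 0.042, which sum to 0.250. Kaplan-Meier gives 1 − e^(−0.2624) = 0.231, or 1.9 points too low.

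| r | h | S | U | Kaplan-Meier mortality | Error (points) |
|---|---|---|---|---|---|
| 0.5 | 0.3042 | 0.236 | 0.014 | 26.2% | +1.2 |
| 1 | 0.2877 | 0.225 | 0.025 | 25.0% | 0 |
| 2 | 0.2624 | 0.208 | 0.042 | 23.1% | −1.9 |
| 3 | 0.2436 | 0.195 | 0.055 | 21.6% | −3.4 |
| 5 | 0.2168 | 0.175 | 0.075 | 19.5% | −5.5 |

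With exits at 10% and 30%, the error is −1.0 and −2.8 points at r = 2, and −1.7 and −4.9 at r = 3. Over 10% to 30% exits and r from 1 to 5, the understatement runs from 0 to 7.8 points.

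**In patients.** At 20% exits and r = 2 to 3, the expected unseen deaths are 0.8 to 1.1 in an arm of 20 (20 × 0.042 and 20 × 0.055) and 0.4 to 0.6 in placebo. One patient is 1/20 = 5 points in a VM202 arm and 1/10 = 10 points in placebo.

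**Without a model.** If nothing is assumed about leavers' later risk, each 10% of an arm with unknown status adds up to 10 points of uncertainty to the 12-month risk.

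**Amputation.** No separate figure is given here. Protocol 1.3.3 gives one-year amputation-free survival (45%), a composite that the SAP does not analyse, and no one-year risk of amputation alone. The amputation curve also censors deaths, which raises the estimated amputation risk above the true cumulative incidence. That can oppose the loss of events among leavers, so the net direction is open.

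**The case against.** A reader might infer that follow-up stops altogether at exit. The documents do not support that. Recorded AEs and SAEs are followed to resolution or stability, SAE reporting asks for hospital records and a death narrative, and the AE window runs nominally to Month 12. Acute limb ischaemia needing intervention would ordinarily be an SAE and so be followed. A death that causes exit is a listed exit reason and is captured. SAP 10.2.7 censors only patients without a reported event, so an amputation reported during that follow-up need not be lost. All of this stands. The gap that remains is a new death or amputation after an exit with no open event, or after the open event has been called stable.

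A reader might also infer that limb worsening in general is an exit criterion. The limb reason is narrower, and it appears only in a SAP table shell, not in Protocol 3.5.2. The AE reason in 3.5.2 is qualified as pre-treatment, so the AE exit for dosed patients also rests mainly on the shell. The link to prognosis is therefore plausible but not established, and for voluntary leavers there is no specific reason to expect 2 to 3 times the hazard.

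The background mortality describes CLI patients in general. The trial excludes patients with NYHA class III or IV heart failure, imminent amputation or short life expectancy, so actual rates may be lower. The protocol also classes mortality and amputation as secondary efficacy endpoints, in a 50-patient study sized for estimation. These points limit the weight of the concern but do not supply the missing status.

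**Conclusion.** The concern holds in a limited form. The available text requires no vital or major-amputation status to Month 12 for dosed patients who leave early, and SAP 10.2.7 censors those without a reported event at discontinuation. Because some exits are plausibly related to prognosis, the censoring may be informative.

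If leavers are at higher risk, mortality is understated by about 2 to 3 points at 20% exits and 2 to 3 times the hazard. That is less than one patient in an arm of 20, and it rests on assumed exit rates, an assumed hazard ratio and the protocol's background mortality. The stronger reading, that 12-month outcomes will look better than they are, is not supported: the error is zero at equal hazard and reverses below it, and the between-arm direction depends on which arm loses more patients. The missing outcome data are a weakness whatever the direction.

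A reader might extend the point to neoplasia. The censoring rule does not cover it, the SAP has no time-to-event analysis of it, and no patient has scheduled cancer screening after baseline, so that gap is not specific to leavers.

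The sample consent form was not available, so any follow-up wording there could not be checked.

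**What to change.** **Protocol 3.5.2.** Separate stopping study visits from withdrawing consent for follow-up. For every dosed patient who has not refused, including those replaced before Day 90, obtain vital status and major amputation (date and side) at Months 6 and 12 by telephone or record check. The same contact may ask about a new neoplasm. Name these outcomes as the purpose of the contacts with patients lost to follow-up.

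**SAP 10.2.7.** Count events found this way. Censor event-free patients at the last date of confirmed status for that outcome, not at study discontinuation. Add a sensitivity analysis that counts limb-related exits as events. Reporting amputation with death as a competing risk would also help.

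**Cost.** A short amendment, consent wording to match, and up to two contacts per leaver, with no added visit or procedure. The downsides are a small site effort and possibly less favourable event rates.
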